Randomized Open-Label Trial to Compare the Immunogenicity of Cell Culture-Based and Recombinant
Unadjuvanted Quadrivalent Influenza Vaccines to Conventional Egg-Based Unadjuvanted Quadrivalent Influenza
Vaccines among Healthcare Personnel Aged 18-64 Years:

Year 2 Protocol Amendment

NCT03722589

Document Date: July 11, 2019

1. Protocol Title

Randomized Open-Label Trial to Compare the Immunogenicity of Cell Culture-Based and Recombinant Unadjuvanted Influenza Vaccines to Egg-Based Influenza Vaccines among Healthcare Personnel Aged 18-65 Years:

Year Two Amendment

Background

The first year of this randomized, open-label trial conducted during the 2018-2019 influenza season assessed humoral and cell-mediated immune responses to cell culture-based and recombinant unadjuvanted quadrivalent influenza vaccines compared to conventional egg-based unadjuvanted quadrivalent SD (SD) (15 μ g of HA per strain) influenza vaccines among healthcare personnel (HCP) aged 18-64 years at two sites in the United States. Eligible participants were randomized 2:2:1:1 to receive a single dose of cell culture-based vaccine (FlucelvaxTM Quadrivalent by Seqirus, Inc., 15 μ g of HA per strain) versus recombinant vaccine (Flublok[®] Quadrivalent by Sanofi Pasteur, 45 μ g of HA per strain) versus one of two egg-based SD vaccines (Fluzone[®] Quadrivalent by Sanofi Pasteur, 15 μ g of HA per strain and Fluarix[®] Quadrivalent by GlaxoSmithKlein, 15 μ g of HA per strain) during October 2018. The first year of the trial was designed to address the question of whether HCP who receive cell culture-based or recombinant influenza vaccines for the first time (after receipt of egg-based SD vaccines in previous seasons) have higher antibody titers (surrogates for immune protection^{1,2}) against circulating influenza viruses compared to HCP who receive egg-based SD vaccines.

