- Indicators of immune response to vaccination based on other immunologic assays not listed above (as appropriate)

METHODS, YEAR TWO MODIFICATIONS

Unless otherwise specified in the sections below, study methods will remain the same as those described in the original protocol.

Inclusion Criteria

- Healthcare personnel, including dentists and other dental health personnel
- Have been receiving routine medical care in the Baylor Scott & White Health System for at least one month before enrolling in the study
or
enrolled in the Kaiser Permanente health network for at least one month before enrolling in the study
- Aged 18-65 years for participants who were originally enrolled in year one of the study
- Aged 18-64 years for participants newly enrolled in year two of the study
- Available and willing to participate in study follow-up through approximately 1 month after study vaccination in the 2019-2020 influenza season
- Received an egg-based SD influenza vaccine during the 2018-2019 influenza season (for participants enrolled for the first-time during year two)

Exclusion Criteria

- Already received an influenza vaccine during the current influenza season
- Previous hypersensitivity reaction to the study vaccines as reported by the subject
- Received any vaccine in the 4 weeks prior to the first study visit or plans to receive a vaccine (other than influenza vaccine provided through the study protocol) in the 4 weeks following the first study visit
- Currently participating in a study that involves an experimental agent (vaccine, drug, biologic, device, blood product, or medication), or has received an experimental agent within 1 month prior to enrollment in this study, or expects to receive an experimental agent during participation in this study
- Any condition that the research staff believes may interfere with successful completion of the study

[figure not shown]
- You are not willing or able to get the licensed flu vaccines being used in this study;
- For enrollment into the non-randomized Fluzone® High-Dose arm at KPNW, the following exclusion criterion will also apply for female HCP aged 18-49 years:
 - Pregnant by participant report or study-administered urine pregnancy test

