Study Design: Year two of the trial will be open-label and will include both randomized and non-randomized arms (Figure 3). Since the proposed trial design is a modification of the original protocol, the consent process will be repeated for all participants from year one of the trial. Participants from year one who received Flucelvax™ Quadrivalent or Flublok® Quadrivalent will be randomized 1:1 to receive Flucelvax™ Quadrivalent or Flublok® Quadrivalent in year two (Figure 3). Participants who received an egg-based SD vaccine in year one (Fluzone® Quadrivalent or Fluarix Quadrivalent) will be randomized 1:1:1 to receive Flucelvax™ Quadrivalent, Flublok® Quadrivalent, or Fluzone® Quadrivalent in year two.

Both sites may also aim to enroll additional participants to achieve a total of 150 participants per site (including participants who continue from year one plus additional newly enrolled participants) who received egg-based SD influenza vaccine during the 2018-2019 influenza season and who will be randomized 1:1:1 to receive Flucelvax™ Quadrivalent, Flublok® Quadrivalent, or Fluzone® Quadrivalent in year two. The KPNW site will also enroll up to 80 new participants for a non-randomized study arm that will receive Fluzone® High-Dose.

The study will prioritize enrollment of HCP who participated in a previous study of influenza vaccine effectiveness that was conducted at both study sites during the 2010-2011 influenza season. Stratified enrollment will be used for both randomized and non-randomized arms to ensure an even mix of age groups (18-44 years and 45-65 years) in each study arm.

Figure 3 Stratified randomization and sample size goals for groups with new enrollees per site

[figure not shown]
[figure not shown]

Figure 4 Study activity flow diagram, Year two

Consent/Screening/Enrollment:

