Participants who present with moderate to severe illness with fever and/or acute illness during the study visit will not receive study vaccine until their illness has resolved. In this case, a follow-up appointment will be made after resolution of the illness, at which time the participant will receive the vaccine.

Randomization of Participants in Year two of the Study

Study nurses administering vaccine will consult participants' study files to confirm which study vaccine participants from year one received during the first year of the study. For the purposes of randomization, newly enrolled participants into the main trial who did not participate in year one will be treated as part of the group who received FluZone® Quadrivalent or Fluarix ® Quadrivalent during year one.

Stratified block randomization will be used at each site to ensure even allocation of age groups (18-44 years and either 45-65 years) to each study arm (Figure 3). Within each age stratum:

- participants who received Flucelvax™ Quadrivalent in year one will be randomized 1:1 to receive one 0.5 mL intramuscular dose Flucelvax™ Quadrivalent or Flublok® Quadrivalent;
- participants who received Flublok® Quadrivalent in year one will be randomized 1:1 to receive one 0.5 mL intramuscular dose of Flucelvax™ Quadrivalent or Flublok® Quadrivalent; and
- participants who received FluZone® Quadrivalent or Fluarix ® Quadrivalent in year one or who were newly enrolled into the main trial will be randomized 1:1:1 to receive one 0.5 mL intramuscular dose of Flucelvax™ Quadrivalent, Flublok® Quadrivalent , or FluZone® Quadrivalent.

Randomization lists will be generated using a computerized random-number generator to select randomly permuted group blocks of six with either three in each block assigned to Flucelvax™ Quadrivalent and Flublok® Quadrivalent for those who received Flucelvax™ Quadrivalent or Flublok® Quadrivalent in year one or two in each block assigned to FluZone® Quadrivalent or Flucelvax™ Quadrivalent or Flublok® Quadrivalent for those who received FluZone® Quadrivalent in year one or are newly enrolled to the main trial in year two. The next available sequential study-number will be assigned to each enrolled participant upon study-entry.

Participants who are newly enrolled into the FluZone® High-Dose substudy will not be randomized and will all receive FluZone® High-Dose.

'Opt-In Consent for Longitudinal PBMC Collection:

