Compare immune responses after two consecutive years of vaccination with cell-based influenza vaccine (Flucelvax™ Quadrivalent) or recombinant influenza vaccine (Flublok® Quadrivalent) versus first time receipt of these vaccines following vaccination with SD egg-based influenza vaccines.	Flucelvax™ Quadrivalent year one/year two	SD egg-based vaccine year one/Flucelvax™ Quadrivalent year two
	Flublok® Quadrivalent year one/year two	SD egg-based vaccine year one/Flublok® Quadrivalent year two
Compare immune responses after two consecutive years of vaccination with cell-based influenza vaccine (Flucelvax™ Quadrivalent), recombinant influenza vaccine (Flublok® Quadrivalent), or SD egg-based vaccine (Fluzone SD).	Flucelvax™ Quadrivalent year one/year two	SD egg-based vaccine year one/year two
	Flublok® Quadrivalent year one/year two	SD egg-based vaccine year one/year two

Compare immune responses after cell culture-based influenza vaccine (Flucelvax™ Quadrivalent) versus recombinant influenza vaccine (Flublok® Quadrivalent) at approximately 28 days after receipt of the 2019-2020 vaccines, regardless of prior vaccination status.	Flucelvax™ Quadrivalent year 2 (regardless of year one vaccine)	Flublok® Quadrivalent year 2 (regardless of year one vaccine)
Compare immune responses after first time vaccination with cell-based influenza vaccine (Flucelvax™ Quadrivalent), recombinant influenza vaccine (Flublok® Quadrivalent), or high-dose egg-based vaccine (Fluzone High-Dose) following vaccination with SD egg-based influenza vaccines to repeated vaccination with SD egg-based vaccine.	SD egg-based vaccine year one/Flucelvax™ Quadrivalent year two SD egg-based vaccine year one/Flublok® Quadrivalent year two Fluzone HD year two	SD egg-based vaccine year one/year two

SD: Standard dose; HD: High dose

Power/Sample Size Calculations:

Study sample size was determined based on available resources. An overall sample size of up to 830 with

- 90 participants each in the Flublok® Quadrivalent year one/ Flucelvax™ Quadrivalent year two group and Flublok® Quadrivalent year one/year two group
- 135 participants each in the Flucelvax™ Quadrivalent year one/year two group and Flucelvax™ Quadrivalent year one/ Flublok® Quadrivalent year two group
- 100 participants each in the SD (SD) egg-based vaccine year one/Flucelvax™ Quadrivalent year two, SD egg-based vaccine year one/Flublok® Quadrivalent year two, and SD egg-based vaccine year one/year two groups, and

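### New enrollees join only the SD-history groups, which dilutes the year-one randomisation behind the Objective 1 and 3 contrasts

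*Combined protocol and SAP*

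**What the plan says.** The Background describes the year-one allocation: "Eligible participants were randomized 2:2:1:1 to receive a single dose of cell culture-based vaccine", with recombinant vaccine and two SD egg-based products as the other arms. Under Study Design for year two, "Both sites may also aim to enroll additional participants to achieve a total of 150 participants per site", and that total is defined as "including participants who continue from year one plus additional newly enrolled participants". New main-trial participants qualify under the Inclusion Criteria by having had an SD egg-based vaccine in 2018-19.

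The section on randomisation in year two states that, for allocation, "newly enrolled participants into the main trial who did not participate in year one will be treated as part of the group who received" one of the two SD egg-based products in year one. SD recipients and those who "were newly enrolled into the main trial will be randomized 1:1:1" share one list. Prior Flucelvax and prior Flublok recipients have their own 1:1 lists. On stratification: "Stratified block randomization will be used at each site to ensure even allocation of age groups". The strata are therefore site, age group and year-one vaccine group; new versus returning is not one of them.

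Table 5 sets two years of Flucelvax or Flublok "versus first time receipt of these vaccines following vaccination with SD egg-based influenza vaccines" (Objective 1), and against SD vaccine in both years (Objective 3). It does not separate new from returning participants. The analysis section has a general provision to adjust by ANOVA where vaccine groups are unbalanced, without naming covariates. It proposes chi-square tests for seroconversion (SCR) and calls the primary analyses intention-to-treat.

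**The concern.** Objectives 1 and 3 ask what the year-one vaccine did to the year-two response. Year-two randomisation takes place within each year-one vaccine group, so it cannot balance groups that come from different lists. Only the year-one allocation spans them. Everyone in the Flucelvax/Flucelvax and Flublok/Flublok groups went through that allocation. Some people in SD/Flucelvax, SD/Flublok and SD/SD may not have: they had their 2018-19 vaccine outside the trial.

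If new and returning healthcare personnel differ in vaccination history, health or pre-vaccination titre, part of that difference enters the contrast and can look like, or hide, an effect of repeat vaccination. The protocol's own rationale says that frequent past vaccination may blunt the antibody response, so vaccination history is a plausible route. The contrasts at stake include the test of the first stated year-two hypothesis.

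**Working it through.** **1. Which randomisation covers which contrast.** Table 5 lists 2 + 2 + 1 + 3 = 8 contrasts.

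| Objective | Contrasts | Randomisation that spans the groups | New enrollees |
|---|---|---|---|
| 1 | 2 | Year one only | One side |
| 3 | 2 | Year one only | One side |
| 2 | 1 | Year two, within each list | Both sides |
| 4, Flucelvax and Flublok | 2 | Year two, within the SD-history list | Both sides |
| 4, High-Dose | 1 | None, by design | All of the High-Dose arm |

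**2. Are new enrollees in the analysis groups, or only on the allocation list?** The sentence on how they are treated concerns allocation. The sample sizes settle the matter: 2 sites × 150 / 3 arms = 100, exactly the SD-history group size in the sample-size section. The total also reproduces: 2×90 + 2×135 + 3×100 + 80 = 830. The Table 5 groups are sized with new enrollees in them.

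**3. Share of new enrollees (assumption).** Under 2:2:1:1 the two SD arms together equal one Flucelvax or one Flublok arm. The year-two targets imply 2×135 = 270 returning Flucelvax and 2×90 = 180 returning Flublok participants. If SD participants return at one of those levels:
- 300 − 270 = 30 new, f = 0.10, leaving 90 returning per SD-history group;
- 300 − 180 = 120 new, f = 0.40, leaving 60 per group.

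**4. Shift of a null contrast.** If new and returning participants differ in day-28 GMT by a ratio r, the contrast moves by r^f. The value of r is assumed; the documents give none. The last two columns show f·ln(r)/ln(1.2).

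| r | r^0.10 | r^0.40 | Share of ln 1.2, f = 0.10 | Share of ln 1.2, f = 0.40 |
|---|---|---|---|---|
| 1.05 | 1.005 | 1.020 | 3% | 11% |
| 1.10 | 1.010 | 1.039 | 5% | 21% |
| 1.25 | 1.023 | 1.093 | 12% | 49% |

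**5. Effect on error rates.** Table 6 states neither the SD of log titre nor the power. A two-sided t-test at 80% power (assumed) fits it with a natural-log SD of 0.292 at 0.05/8 (16/22/34/68/242) or 0.297 at 0.05/7 (16/22/34/69/245, exact). With SD 0.295, r = 1.2 and nominal 0.00625 per test, the false-positive rate is about 0.011–0.012 at f = 0.10 and 0.15–0.19 at f = 0.40. With an assumed SD of 1.0 it is about 0.007 and 0.013–0.015. The consequence therefore depends heavily on the true spread of titres.

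**6. Precision cost of the remedies.** The planned variance factor is 1/n₁ + 1/100, with n₁ = 135 (Flucelvax/Flucelvax) or 90 (Flublok/Flublok).
- Returning only: 1/n₁ + 1/(100(1−f)). For n₁ = 135 and f = 0.40, √[(1/135 + 1/60)/(1/135 + 1/100)] = 1.18; for f = 0.10, 1.03. For n₁ = 90: 1.15 and 1.03.
- Indicator in a pairwise model: new enrollees are on one side only, so the factor is again 1/135 + 1/60. Nothing is saved.
- Indicator common to the three SD-history arms (equal new shares): 1/n₁ + 1/100 + f/(300(1−f)). For n₁ = 135 and f = 0.40, √[(0.00741 + 0.01222)/(0.00741 + 0.01000)] = 1.06; for f = 0.10, 1.01. For n₁ = 90: 1.05 and 1.01.

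**The case against.** New enrolment is optional, and continuing SD participants keep their year-one allocation. New enrollees work in healthcare at the same two sites and did receive the exposure that Objective 1 specifies. The plan allows adjustment for imbalance, collects ten years of vaccination history for new enrollees, and includes mean-fold rise and SCR, which are relative to day 0. Their different upper age limit (64 against 65) mostly reflects the year-one cohort ageing by a year. Figure 3, whose title refers to groups with new enrollees, and the original protocol could not be read here; either may give enrolment goals or covariates.

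Most of this stands and limits the size of the point. It does not remove it. A provision that names no covariate does not commit the analysis to handling new status, the vaccination history is tied to no model, and chi-square tests adjust for nothing. Endpoints relative to baseline are not immune to differences in vaccination history.

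A second objection is that the returning-only comparison is not fully randomised either, because return requires renewed consent after an open-label year. That is correct. The targets of 270 and 180 from two equally allocated arms suggest that return or year-one enrolment may have been unequal. The returning-only analysis is therefore better placed beside the adjusted estimate than in its place.

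**Conclusion.** The point holds as a dilution. In four of the eight Table 5 contrasts, any new enrollees sit on one side without year-one randomisation, and no stratum, restriction or named covariate deals with it. With a new share of 10–40% and a new/returning GMT ratio of 1.05–1.25, both assumed, a null contrast moves to about 1.005–1.09. At the low end this is negligible; at the high end it is about half of the log ratio that the trial is sized to detect.

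A reader might infer more than the documents support:
- That the year-one randomisation is lost. It is weakened in proportion to the new share, and not at all if no one new is enrolled.
- That new enrollees' exposure is misclassified. They must have had an SD egg-based vaccine in 2018-19; the issue is comparability.
- That stratifying the year-two lists by new/returning status would cure it. That would equalise new shares across the three SD-history arms but leave new enrollees on one side in Objectives 1 and 3.

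Objective 2 and the Flucelvax and Flublok parts of Objective 4 are unaffected.

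**What to change.** For the Objective 1 and 3 contrasts:
1. Fit one model across the randomised year-two arms with baseline titre, age group, site and a new/returning indicator common to the three SD-history arms. Leave the High-Dose arm out of this model, since all its participants are new.
2. Replace the chi-square test for SCR with the analogous adjusted model, for example logistic regression with the same terms.
3. Prespecify the same contrasts in participants randomised in year one only, and report them alongside.

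Keep new enrollees in full for Objective 2 and the randomised parts of Objective 4.

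The cost is wording in Table 5 and the analysis section, plus some precision: the standard error rises about 1–6% with the joint indicator, before any gain from baseline titre, and about 3–18% in the returning-only analysis. At the SD back-solved from Table 6 (0.295), a ratio of 1.2 and 0.05/8, returning-only power is 89–96% instead of 97% for Flucelvax/Flucelvax, and 82–91% instead of 93% for Flublok/Flublok. The joint indicator assumes that the new/returning difference is the same in all three SD-history arms; the returning-only analysis does not need this but keeps the selection from repeat consent.

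One detail to settle: the year-two day-0 titre is measured after the year-one vaccine. Adjusting for it removes any year-one effect carried by residual antibody, so the plan should state which effect is wanted and also show the estimate without it.

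### One fixed block length of six in an open-label trial makes up to 25% (1:1 lists) or 20% (1:1:1 lists) of allocations predictable to anyone who sees a whole list

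*Combined protocol and SAP*

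**What the plan says.** The section on randomization in year two gives one block length: the program will "select randomly permuted group blocks of six". The composition follows from the ratio. For year-one Flucelvax or Flublok recipients the blocks are built "with either three in each block assigned to Flucelvax™ Quadrivalent and Flublok® Quadrivalent", that is 3+3. For year-one egg-based recipients and new enrollees they are built "or two in each block assigned to FluZone® Quadrivalent or Flucelvax™ Quadrivalent or Flublok® Quadrivalent", that is 2+2+2. No second length is mentioned.

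On the lists themselves, "Stratified block randomization will be used at each site to ensure even allocation of age groups", and within each age stratum there is a separate scheme for each year-one vaccine group. The nurses who vaccinate look up the year-one vaccine, so they know which list applies. On order of entry: "The next available sequential study-number will be assigned to each enrolled participant upon study-entry".

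On masking, Study Design states: "Year two of the trial will be open-label and will include both randomized and non-randomized arms". For vaccine administration and blinding procedures the amendment refers back to year one, and methods that it does not restate also stay as in the original protocol. That protocol was not available for this review.

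**The concern.** With a known, constant block length and open past allocations, the last places of a block follow from those already filled. Whoever enrols or schedules participants could then know the next vaccine before deciding who comes next. Laboratory endpoints guard against biased assessment of outcome, but not against selection at entry.

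The two kinds of list are not equally exposed. The 1:1 lists are a closed cohort of year-one participants, so only their order of entry could be influenced. On the 1:1:1 lists new enrollees and returners share the same sequence, and the sites recruit the new enrollees. Steering is more feasible there. Those lists feed the comparisons of first-time Flucelvax or Flublok with repeated standard-dose egg-based vaccine in Table 5, and they contribute to the overall Flucelvax versus Flublok comparison.

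**Working it through.** The plan states no predictability figure to reproduce. Its block composition is consistent with its ratios: 6/2 = 3 per arm and 6/3 = 2 per arm.

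**Inputs**
- Block length 6, as 3+3 or 2+2+2 (section on randomization in year two).
- Planned sizes (Power/Sample Size Calculations): 1:1 lists 2 × 135 + 2 × 90 = 450; 1:1:1 lists 3 × 100 = 300; total 750 randomised.
- Assumption for the ceiling: the observer knows the block length and has seen every earlier allocation on that list.

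**Ceiling on 1:1 lists.** An allocation is certain when all remaining places in the block belong to one arm. Over the 20 distinct orderings of a 3+3 block, the number of certain places is 1 with probability 3/5, 2 with 3/10 and 3 with 1/10. The mean is 0.6 + 0.6 + 0.3 = 1.5, and 1.5/6 = 25%. The closed form for a block of 2m gives the same: 1/(m+1) = 1/4.

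**Ceiling on 1:1:1 lists.** Over the 90 distinct orderings of a 2+2+2 block, the number is 1 with probability 4/5 and 2 with 1/5. The mean is 0.8 + 0.4 = 1.2, and 1.2/6 = 20%.

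**Total.** 0.25 × 450 + 0.20 × 300 = 112.5 + 60 = 172.5, so about 172 of 750 (23%). Incomplete last blocks lower this a little. If each group splits equally over four site-by-age lists, the shares are 16.5/67 = 24.6% (year-one Flucelvax), 10.5/45 = 23.3% (year-one Flublok) and 14.4/75 = 19.2% (1:1:1).

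**Simple guessing.** Always naming the arm with most places left is right 41/60 = 68.3% of the time on 1:1 lists (50% by chance), and 101/180 = 56.1% on 1:1:1 lists (33.3% by chance).

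**Partial sight.** Suppose each earlier allocation is seen independently with a given probability, and block boundaries are still known (assumed fractions):

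| Earlier allocations seen | 1:1 certain | 1:1:1 certain |
|---|---|---|
| 100% | 25% | 20% |
| 75% | 10.5% | 6.3% |
| 50% | 3.1% | 1.3% |

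**Possible size of bias (illustration; d is assumed).** Suppose that at every certain place staff raise the expected titer by a factor d when one arm is due and lower it by d when the other is due. With a certain share c, the GMT ratio is distorted by d^(2c). For 1:1:1 lists with full sight, 2c = 0.4: d = 1.1 gives 1.04 and d = 1.2 gives 1.08. For 1:1 lists, 2c = 0.5: 1.05 and 1.10. At 50% sight on 1:1:1 lists, 2c = 0.025 and d = 1.2 gives 1.005. The plan's target GMT ratio is 1.2.

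**Effect of mixed lengths.** Lists of 60 were simulated with equally likely lengths and an observer who knows the set of lengths. With 4/6/8 on 1:1 lists, certain allocations fall from 25% to about 2%, and the guess rate is 0.68. With 6/9/12 on 1:1:1 lists, they fall from 20% to about 2%, and the guess rate is about 0.52.

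**The case against.** Blocks of six are ordinary practice, and nothing in this section is contradictory or in error. The percentages need a person who knows the block length and follows an entire list. The documents do not say how many nurses vaccinate, who holds the lists or which site staff read the amendment. All of that stands, which is why the figures are given as ceilings.

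The year-one protocol may set out who holds the lists and when an allocation is revealed. That also stands, and those details decide whether anyone choosing participants could use the information. Sealed or central allocation would not by itself remove the predictability, however, because past allocations are open and the block length is constant.

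No motive or usable predictor is shown either. The documents do not say that staff hold titers for the person in front of them at visit 1. Fold rise and seroconversion are relative to baseline, and the analysis section plans ANOVA to adjust for imbalances between vaccine groups. This handles much of any measured imbalance, though not an unmeasured one.

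A reader might infer more: that vaccinating staff do know a quarter of upcoming allocations, that allocation is unconcealed, or that the randomised comparisons are biased. The documents support none of these. The quarter is a maximum, and it applies to the closed 1:1 cohort rather than to the lists that take new enrollees. The silence on concealment may only reflect the reference back to year one.

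**Conclusion.** The point holds as a minor one. A single fixed block length, open allocations and identifiable lists allow at most 25% of 1:1 allocations and at most 20% of 1:1:1 allocations to be known in advance. That rests on full sight of each list and on knowledge of the block length; with half the earlier allocations seen, the shares drop to about 3% and 1%. What is shown is an opportunity for selection. Any resulting bias in the GMT ratios is probably small, and the larger distortions illustrated above would require deliberate steering at every predictable place. The conclusion about opportunity does not depend on the year-one procedures; how far it could be used does.

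**What to change.** Generate each list with block lengths chosen at random from a set that keeps the ratio, for example 4, 6 and 8 for the 1:1 lists and 6, 9 and 12 for the 1:1:1 lists. Move the lengths out of the protocol into a restricted randomisation document. In the protocol, say only that permuted blocks of varying length are used, and state or cross-refer to the concealment procedure.

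The cost is a change to the list program before the lists are made, with no extra participants, visits or assays. One downside is slightly larger possible imbalance where a list stops mid-block. The largest difference between two arms rises from 3 to 4 on a 1:1 list (half of 6 against half of 8) and from 2 to 4 on a 1:1:1 list (a third of 6 against a third of 12). With about 45 to 75 participants per list this matters little. The other limit is that the change removes most certain knowledge but leaves the simple guess rate almost where it was.
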